8.1 Adverse events

[figure not shown]
8.1.1 Definitions and reporting

An adverse event is defined as the appearance of (or worsening of any pre-existing) undesirable sign(s), symptom(s), or medical condition(s) that occur after patient’s signed informed consent has been obtained. Abnormal laboratory values or test results occurring after informed consent constitute adverse events only if they induce clinical signs or symptoms, are considered clinically significant, require therapy (e.g., hematologic abnormality that requires transfusion or hematological stem cell support), or require changes in study medication(s).

For patients who sign the ICF, all AEs will be captured in the AE eCRF from time of signature through 30 days after permanent study drug discontinuation. For patients who fail screening, only SAEs will be captured in the AE eCRF page.

Adverse events that begin or worsen after informed consent should be recorded in the Adverse Events eCRF. Conditions that were already present at the time of informed consent should be recorded in the Medical History page of the patient’s CRF. Adverse event monitoring should be continued for at least 30 days (or 5 half-lives, whichever is longer) following the last dose of study treatment. Adverse events (including lab abnormalities that constitute AEs) should be described using a diagnosis whenever possible, rather than individual underlying signs and symptoms. When a clear diagnosis cannot be identified, each sign or symptom should be reported as a separate Adverse Event.

Adverse events will be assessed according to the Common Terminology Criteria for Adverse Events (CTCAE) version 4.03. If CTCAE grading does not exist for an adverse event, the

severity of mild, moderate, severe, and life-threatening, corresponding to Grades 1 - 4, will be used. CTCAE Grade 5 (death) will not be used in this study; rather, information about deaths will be collected on the appropriate eCRF.

The occurrence of adverse events should be sought by non-directive questioning of the patient (subject) during the screening process after signing informed consent and at each visit during the study. Adverse events also may be detected when they are volunteered by the patient (subject) during the screening process or between visits, or through physical examination, laboratory test, or other assessments. As far as possible, each adverse event should be evaluated to determine:

1. The severity grade (CTCAE Grade 1-4)
2. Its duration (Start and end dates)
3. Its relationship to the study treatment (Reasonable possibility that AE is related: No, Yes)
4. Action taken with respect to study or investigational treatment (none, dose adjusted, temporarily interrupted, permanently discontinued, unknown, not applicable)
5. Whether medication or therapy taken (no concomitant medication/non-drug therapy, concomitant medication/non-drug therapy)
6. Outcome (not recovered/not resolved, recovered/resolved, recovering/resolving, recovered/resolved with sequelae, fatal, unknown)
7. Whether it is serious, where a serious adverse event (SAE) is defined as in [Section 8.2.1](#).

All adverse events should be treated appropriately. If a concomitant medication or non-drug therapy is given, this action should be recorded on the Adverse Event CRF.

Once an adverse event is detected, it should be followed until its resolution or until it is judged to be permanent, and assessment should be made at each visit (or more frequently, if necessary) of any changes in severity, the suspected relationship to the study treatment, the interventions required to treat it, and the outcome.

Progression of malignancy (including fatal outcomes), if documented by use of appropriate method (for example, as per RECIST criteria for solid tumors or as per Cheson's guidelines for hematological malignancies), should not be reported as a serious adverse event.

Adverse events separate from the progression of malignancy (example, deep vein thrombosis at the time of progression or hemoptysis concurrent with finding of disease progression) will be reported as per usual guidelines used for such events with proper attribution regarding relatedness to the drug.

8.1.2 Laboratory test abnormalities

8.1.2.1 Definitions and reporting

Laboratory abnormalities that constitute an Adverse event in their own right (are considered clinically significant, induce clinical signs or symptoms, require concomitant therapy or require changes in study treatment), should be recorded on the Adverse Events CRF. Whenever possible, a diagnosis, rather than a symptom should be provided (e.g. anemia instead of low hemoglobin). Laboratory abnormalities that meet the criteria for Adverse Events should be followed until they have returned to normal or an adequate explanation of

the abnormality is found. When an abnormal laboratory or test result corresponds to a sign/symptom of an already reported adverse event, it is not necessary to separately record the lab/test result as an additional event.

Laboratory abnormalities, that do not meet the definition of an adverse event, should not be reported as adverse events. A Grade 3 or 4 event (severe) as per CTCAE does not automatically indicate a SAE unless it meets the definition of serious as defined below and/or as per investigator's discretion. A dose hold or medication for the lab abnormality may be required by the protocol in which case the lab abnormality would still, by definition, be an adverse event and must be reported as such.

8.2 Serious adverse events

8.2.1 Definitions

Serious adverse event (SAE) is defined as one of the following:

- Is fatal or life-threatening
- Results in persistent or significant disability/incapacity
- Constitutes a congenital anomaly/birth defect
- Is medically significant, i.e., defined as an event that jeopardizes the patient or may require medical or surgical intervention to prevent one of the outcomes listed above
- Requires inpatient hospitalization or prolongation of existing hospitalization, unless hospitalization is for:
 - Routine treatment or monitoring of the studied indication, not associated with any deterioration in condition
 - Treatment on an emergency outpatient basis for an event not fulfilling any of the definitions of a SAE given above and not resulting in hospital admission
 - Elective or pre-planned treatment for a pre-existing condition that is unrelated to the indication under study and has not worsened since signing the informed consent
 - Social reasons and respite care in the absence of any deterioration in the patient's general condition
- Protocol exempt SAEs: Any SAEs that are expected due to the condition being treated and where there has been a clear agreement with regulators not to collect these SAEs in the safety database, provided the information is collected elsewhere. For example, this may include serious adverse events that are also a primary outcome measure, such as mortality, survival rate or number of flares of the condition being studied.

8.2.2 Reporting

To ensure patient safety, every SAE, **regardless of suspected causality**, occurring after the patient has provided main informed consent and until at least 30 days after the patient has stopped study treatment must be reported to Novartis within 24 hours of learning of its occurrence.

SAE collection starts at time of main ICF signature whether the patients is a screen failure or not.

Any SAEs experienced after this 30 days period should only be reported to Novartis if the investigator suspects a causal relationship to the study treatment. Recurrent episodes, complications, or progression of the initial SAE must be reported as follow-up to the original episode within 24 hours of the investigator receiving the follow-up information. An SAE occurring at a different time interval or otherwise considered completely unrelated to a previously reported one should be reported separately as a new event.

Information about all SAEs is collected and recorded on the Serious Adverse Event Report Form within the remote data capture (RDC) system (where available or on the paper SAE form; all applicable sections of the form must be completed in order to provide a clinically thorough report. The investigator must assess and record the relationship of each SAE to each specific study treatment (if there is more than one study treatment), complete the SAE Report Form in English, and send the completed, signed form by fax within 24 hours to the oncology Novartis Drug Safety and Epidemiology (DS&E) department.

When SAEs are recorded electronically in the RDC system, these should be entered, saved and e-signed **within 24 hours of awareness of the SAE**. These data will automatically be submitted to Novartis Drug Safety & Epidemiology immediately after investigator signature or 24 hours after entry, whichever occurs first.

[figure not shown]
The telephone and telefax number of the contact persons in the local department of Drug Safety and Epidemiology (DS&E), specific to the site, are listed in the investigator folder provided to each site. The original copy of the SAE Report Form and the fax confirmation sheet must be kept with the case report form documentation at the study site.

Follow-up information is sent to the same contact(s) to whom the original SAE Report Form was sent, using a new SAE Report Form stating that this is a follow-up to the previously reported SAE and giving the date of the original report. Each re-occurrence, complication, or progression of the original event should be reported as a follow-up to that event regardless of when it occurs. The follow-up information should describe whether the event has resolved or continues, if and how it was treated, whether the blind was broken or not, and whether the patient continued or withdrew from study participation.

If the SAE is not previously documented in the Investigator's Brochure or Package Insert (new occurrence) and is thought to be related to the Novartis study treatment, an oncology Novartis Drug Safety and Epidemiology (DS&E) department associate may urgently require further information from the investigator for Health Authority reporting. Novartis may need to issue an Investigator Notification (IN), to inform all investigators involved in any study with the same drug that this SAE has been reported. Suspected Unexpected Serious Adverse Reactions (SUSARs) will be collected and reported to the competent authorities and relevant ethics committees in accordance with Directive 2001/20/EC or as per national regulatory requirements in participating countries.

8.3 Emergency unblinding of treatment assignment

Not applicable.

8.4 Pregnancies

To ensure patient safety, each pregnancy occurring while the patient is on study treatment must be reported to Novartis within 24 hours of learning of its occurrence. The pregnancy should be followed up to determine outcome, including spontaneous or voluntary termination, details of the birth, and the presence or absence of any birth defects, congenital abnormalities, or maternal and/or newborn complications.

Pregnancy should be recorded on a Clinical Trial Pregnancy Form and reported by the investigator to the oncology Novartis Drug Safety and Epidemiology Department (DS&E). Pregnancy follow-up should be recorded on the same form and should include an assessment of the possible relationship to the study treatment of any pregnancy outcome. Any SAE experienced during pregnancy must be reported on the SAE Report Form.

Pregnancy outcomes must be collected for the female partners of any males who took study treatment in this study. Consent to report information regarding these pregnancy outcomes should be obtained from the mother.

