The major changes included in this amendment include: Addition of an exploratory endpoint to assess the levels of LDE225 in bone marrow, updates to the guidance for contraception based on a recent population pharmacokinetic analysis and updates to the muscle toxicity section for CK elevation.

[figure not shown]
Changes to contraception language

The recommendation for contraception duration has been updated based on a recent population pharmacokinetic analysis that showed a longer half-life of sonidegib in cancer patients (28 days) than in healthy subjects (10 days). Duration of pregnancy prevention was estimated via population pharmacokinetic model-based simulations incorporating the emerging data in cancer patients. The recommended duration of pregnancy prevention in female patients was extended from 6 months to 20 months to ensure the residual plasma sonidegib concentration is reduced below the safety threshold of 3pg/mL. The recommended condom use for 6 months for male patients with partners of child-bearing potential did not change as the 6-month duration is considered adequate to minimize any risk of sonidegib being transmitted to female partners via the seminal fluid of male patients. Female patients of child-bearing potential who had discontinued sonidegib before the current protocol amendment were informed of the need for extended contraception for 20 months.

Changes to the protocol:

The following sections have been changed in the amended protocol:

Changes to the title page:

- The LDE225 International Nonproprietary Name (INN), sonidegib, added.
- Author list updated.

List of abbreviations updated.

Glossary of terms updated.

Protocol summary (Purpose and rationale): Updated number of countries INC424 is approved in.

Protocol summary (Exclusion criteria): revised aspirin dose to 150mg/day to be consistent with other INC424 studies.

Protocol summary (Other assessments): Inserted ‘Bone marrow aspirate samples for pharmacokinetic and pharmacodynamic analysis.

Section 1.4.1.2.1: Updated the total number of subjects, including patients that were dosed with LDE225 as of the most recent Investigator Brochure.

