The majority of adverse effects observed in the 4-wk Good Laboratory Practice (GLP) toxicity studies in growing rats and dogs can be attributed to the pharmacologic action of LDE225, and the effects in both species were similar. The most striking effects of LDE225 were on growing bone, and consisted of thinning or closure of growth plates in the sternum and femur. These effects are not likely to occur in the adult cancer patient population due to the maturity of their skeletal system. Likewise, effects on growing teeth in rats including dentine dysplasia of the incisors is not expected to occur in adult cancer patients. Other drug-related effects, likely associated with the pharmacology of LDE225, included effects on the male and female reproductive tract of young rats and dogs. Gastrointestinal (GI) toxicity was likely dose limiting in the animal studies. In the GLP juvenile rat study, minimal to slight degeneration of nerve fibers was found in the sciatic nerve and, less commonly, in the thoracic spinal cord, but not in the cervical or lumbar spinal cord or optic nerve. Effects on nerves were not seen in any of the toxicity studies on more mature rats or dogs. Consistent with the role of Hh signaling in embryo-fetal development, LDE225 was shown to be teratogenic, an expected class effect of Smo inhibitors. LDE225 was not genotoxic in studies conducted *in vitro* and *in vivo*, and showed no potential risk for phototoxicity.

For more details on the non-clinical toxicity, toxicokinetics and safety of LDE225 refer to the [LDE225 Investigator's Brochure].

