 11. Patients who have neuromuscular disorders (e.g. inflammatory myopathies, muscular dystrophy, amyotrophic lateral sclerosis and spinal muscular atrophy) or are on concomitant treatment with drugs that are recognized to cause rhabdomyolysis, such as HMG CoA inhibitors (statins), clofibrate and gemfibrozil. Pravastatin may be used if necessary, with extra caution.
 12. Patients who plan on embarking on new (or unaccustomed) physical activities, such as strenuous exercise, that can result in significant increases in blood CK levels while on study treatment. NOTE: As a precaution, strenuous muscular activity should be avoided for at least 1 week prior to testing for blood CK levels.

13. Use of other investigational drugs within 30 days of or 5 half-lives of initiation of study treatment, whichever is longer.
14. Patients who are receiving treatment with medications known to be moderate and strong inhibitors or inducers of CYP3A4/5 or drugs metabolized by CYP2B6 or CYP2C9 that have narrow therapeutic index, and that cannot be discontinued before starting treatment with LDE225. Medications that are strong CYP3A4/5 inhibitors should be discontinued at least 7 days and strong CYP3A4/5 inducers for at least 2 weeks prior to starting treatment with LDE225.
15. Pregnant or nursing (lactating) women, where pregnancy is defined as the state of a female after conception and until the termination of gestation, confirmed by a positive hCG laboratory test (> 5 mIU/mL).
16. Patients who are not willing to apply highly effective contraception during the study and through the duration as defined below after the final dose of study treatment.

Women of child-bearing potential, defined as all women physiologically capable of becoming pregnant, must use highly effective contraception during the study and through **20 months** after the final dose of study treatment. Highly effective contraception is defined as either:

- Total abstinence: When this is in line with the preferred and usual lifestyle of the patient. Periodic abstinence (e.g., calendar, ovulation, symptothermal, post-ovulation methods) and withdrawal are not acceptable methods of contraception,
- Sterilization: Patient has had surgical bilateral oophorectomy (with or without hysterectomy) or tubal ligation at least six weeks before taking study treatment. In case of oophorectomy alone, only when the reproductive status of the woman has been confirmed by follow up hormone level assessment,

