- Male partner sterilization (with the appropriate post-vasectomy documentation of the absence of sperm in the ejaculate). [For female study patients, the vasectomised male partner should be the sole partner for that patient],
- Use a combination of the following (both a+b):
 - a. Placement of a non-hormonal intrauterine device (IUD) or non-hormonal intrauterine system (IUS),
 - b. Barrier method of contraception: Condom or Occlusive cap (diaphragm or cervical vault caps) with spermicidal foam/gel/film/cream/vaginal suppository.

Note:

- i) Hormonal contraception methods (e.g. oral, injected, implanted) are not allowed as it cannot be ruled out that the study drug decreases the effectiveness of hormonal contraception.
- ii) Women are considered post-menopausal and not child bearing potential if they have had 12 months of natural (spontaneous) amenorrhea with an appropriate clinical profile (e.g. age appropriate, history of vasomotor symptoms) or six months of spontaneous amenorrhea with serum FSH levels > 40 mIU/mL and estradiol < 20 pg/mL or have had surgical bilateral oophorectomy (with or without hysterectomy) at least six weeks ago. In the case of oophorectomy alone, only when the reproductive status of the woman has been confirmed by follow up hormone level assessment is she considered not of child bearing potential.

- iii) **Male patient** must use highly effective (double barrier) methods of contraception (e.g., spermicidal gel plus condom) for the entire duration of the study, and continue to use contraception and refrain from fathering a child for 6 months following the last dose of study drug. A condom is also required to be used by vasectomized men in order to prevent delivery of the study treatment via seminal fluid.
17. Inability to understand the protocol requirements, instructions and related restrictions, the nature, scope and possible consequences of the study.
18. Unlikely to comply with the protocol requirements, instructions and study related restrictions (e.g. uncooperative attitude, inability to return for follow up visits, psychological illness, and improbability of completing the study).

6 Treatment

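### A female patient's own pregnancy must be reported only if it occurs on treatment, although the contraception period for this teratogenic drug runs 20 months past the last dose

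*Protocol*

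**What the plan says.** Protocol Section 8.4 sets the reporting duty: "each pregnancy occurring while the patient is on study treatment must be reported to Novartis within 24 hours". Follow-up to outcome, including pregnancy loss and birth defects, is then required for a pregnancy so reported. A later sentence in the same section deals with partners: "Pregnancy outcomes must be collected for the female partners of any males who took study treatment in this study". It has no time limit.

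Section 5.3, criterion 16, sets the contraception periods. Women of child-bearing potential "must use highly effective contraception during the study and through 20 months after the final dose of study treatment". Male patients must use contraception and "refrain from fathering a child for 6 months following the last dose of study drug".

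The reason for the female period is given in two places. Section 1.4.1.1.2 states that "LDE225 was shown to be teratogenic, an expected class effect of Smo inhibitors". The Amendment 1 rationale refers to a "longer half-life of sonidegib in cancer patients (28 days) than in healthy subjects (10 days") and ties the 20 months to residual plasma drug falling below a safety threshold of 3 pg/mL. That rationale is used here only as background; the 20-month period itself is current text in Section 5.3.

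**The concern.** The protocol treats the 20 months after the last dose as a time when residual drug could still harm a fetus, yet the pregnancy report stops when treatment stops. A woman who conceives two or twelve months after her last dose is inside the period that Section 5.3 protects and outside the one that Section 8.4 covers. Followed as written, the site has no duty to report that pregnancy, so the follow-up to outcome in Section 8.4 is not triggered either.

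What would be lost is information on pregnancies with possible drug exposure. Such events will be rare in this population, so each unreported one is hard to replace. Normal outcomes and losses that nobody attributes to the drug would go unrecorded, leaving no denominator for any defect that is reported.

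**Working it through.** The plan gives no figure to reproduce. The check sets the reporting window beside the contraception window, then looks for any other rule that closes the difference.

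**Step 1: length of the post-dose period for women.** Section 5.3 gives 20 months. With the SAP's month of 30.4375 days (SAP 2.1.10), 20 × 30.4375 = 608.75 days.

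**Step 2: overlap with Section 8.4.** The duty covers pregnancies occurring on study treatment. Days of the 608.75 covered: 0.

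**Step 3: other rules that might apply.**
- *Section 7.2.2.5.6.* Serum testing is required at end of treatment. The instruction to complete a pregnancy form is written for a patient who must stop treatment because of the pregnancy, so for one still being treated. No test is scheduled after end of treatment.
- *Section 7.1.5.* Patients are contacted 30 days after the last dose. Pregnancy is not among the items listed, and the contact may be waived if treatment continues in another setting.
- *Section 8.1.1.* Adverse events are monitored for at least 30 days or five half-lives, whichever is longer. Pregnancy is not mentioned.
- *Sections 8.2.1 and 8.2.2.* A birth defect is a serious adverse event; a pregnancy in itself is not. Beyond 30 days, a serious event is reported only if the investigator suspects the study treatment. A defect found at birth after a post-treatment conception falls well beyond 30 days, so it depends on that suspicion.
- *Section 11.3.* The consent text asks for adherence to contraception for the duration of the study and does not mention the post-dose periods in Section 5.3. This is a related mismatch.

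None of these requires a report of a female patient's own post-treatment pregnancy.

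**Step 4: the most generous readings.** Suppose the general safety windows did pick up pregnancies.
- 30-day contact: (608.75 − 30) / 608.75 = 578.75 / 608.75 = 95% still uncovered.
- Five half-lives at 28 days: 5 × 28 = 140 days; (608.75 − 140) / 608.75 = 468.75 / 608.75 = 77% uncovered.
- Five half-lives at 10 days, the healthy-subject value: 50 days; 558.75 / 608.75 = 92% uncovered.

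**Step 5: scale only.** Under simple first-order decay with a 28-day half-life, the fraction of drug left at day 30 is 2^(−30/28) = 0.48. The 20 months span 608.75 / 28 = 21.7 half-lives. This assumes a single compartment, whereas the protocol's 20 months came from population pharmacokinetic simulation against a threshold. The fraction shows that drug persists; it does not measure fetal risk or the size of the reporting gap.

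**The case against.** The strongest reply is that the gap is narrow and partly covered. A birth defect is a serious adverse event with no end date for reporting once the drug is suspected, and for a drug that the protocol calls teratogenic, suspicion inside the contraception period is likely. Patients are tested at end of treatment and contacted at 30 days. Few will be able to conceive: Section 1.1 gives a median age at diagnosis of 65, about 82 patients were planned (Section 10.8), and the SAP (Section 1.1) records that Phase II Stage 2 did not open. A 20-month duty would also outlast the last scheduled contact and could outlast the study, which may end 30 days after the last patient discontinues (Section 4.3.2).

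Most of this stands, and it limits the size of the point. It does not remove it. The late-event route needs a defect, knowledge of it and a suspicion of causality, and it records neither the pregnancy nor a normal outcome. The protocol enrols from age 18 and provides for women of child-bearing potential throughout.

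A reader might infer three stronger claims that the documents do not support.
- *That partner pregnancies are also confined to treatment.* The partner sentence in Section 8.4 is open-ended, and adding a 6-month limit could narrow it.
- *That Amendment 1 lengthened the men's period too.* Its rationale says the 6 months did not change and was judged adequate.
- *That nothing after 30 days is captured.* Suspected birth defects are.

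**Conclusion.** The point holds for female patients' own pregnancies. Section 8.4 covers none of the 20-month post-dose period in Section 5.3, and no other section fills the gap. Even if the general adverse-event windows are read as covering pregnancy, between 77% and 95% of the period stays outside them.

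This rests on reading Section 8.4 literally and on the supplied documents. The consent form is a separate document and was not available, so it may already ask patients to tell the site of a later pregnancy.

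The number of patients affected cannot be calculated from the documents and is probably very small. The primary endpoint, the interim decision and the dose determination are untouched. It should be corrected because it concerns safety reporting for a known teratogen and the correction is cheap.

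**What to change.** Reconcile Section 8.4 with Section 5.3. For female patients, a pregnancy arising during treatment, or during the post-treatment contraception period that Section 5.3 already states, should be reported within 24 hours of the site learning of it and followed to outcome. A cross-reference to Section 5.3 is better than repeating the number, so that the two cannot drift apart.

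Leave the partner sentence in Section 8.4 without a time limit. Bring the contraception wording in Section 11.3 into line with Section 5.3.

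State that the duty is passive: the site reports what it learns, and the restriction on contact after withdrawal of consent (Section 7.1.4) still applies. Say also how reports are to be made after the 30-day contact and after the study has closed, since the period can outlast both.

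The cost is a sentence or two in Section 8.4, a consent line, and a longer reporting duty for sites. No visits, tests or analyses are added.
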